#### Statistical Analysis:

Primary outcomes will be measured by:

Difference in proportion (before vs after intervention) in SDOH status and resilience score.

Secondary outcomes will be measured by:

Difference in number of hospitalizations in the 12 months before vs 12 months during intervention, difference in number of ER visits in the 12 months before vs 12 months during intervention, difference in number of primary care visits in the 12 months before vs 12 months during intervention, difference in proportion (before vs after intervention) of patients answering that they perceive they have access to nutritious food, difference in proportion (before vs after intervention) of patients answering that they perceive they have access to nutritious food.

Baseline patient demographics and clinical characteristics will be descriptively summarized. Differences in categorical endpoints before vs after the intervention will be tested using McNemar's test for paired proportions, or exact McNemar's test for small sample sizes. Differences in continuous endpoints before vs after the intervention will be tested using paired t-tests, or appropriate non-parametric test.

The semistructured interview (qualitative data) will be analyzed separately for significant impact, trend and analysis.

Provider data that are recruited for analysis of burnout will be analyzed in difference in proportion to responses pre/post on the Maslach Burnout Inventory. Given the # (10) of participants in this section, we do not expect to reach statistical significance (due to inadequate power) but we will use this as an exploratory outcome.

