**Describe the planned research approach including the community engagement approach (13,500 characters):**

**Describe approach**

We will partner with a Federally Qualified Health Center (FQHC) at Valleywise health to identify and recruit patients into the study. Valleywise health is the largest safety-net healthcare organization in Arizona, serving over 430,000 ambulatory visits per year. They serve a patient population that is medically complex with challenging social barriers to healthcare including homelessness, substance abuse, food insecurity, illiteracy, etc. The healthcare team (providers and social workers) are often challenged by limited community resources to assist patient's through SDOH challenges.

We aim to recruit 30 patients (total) into this study to power the results sufficiently. These patients will have an identified SDOH need that is negatively impacting their health (as determined by the FQHC staff). Once referred, the patient will be screened with a SDOH screening tool (the CMS Accountable Health Communities Screening Tool) to establish a

baseline and interviewed to determine their individual needs, they will also complete the Brief Resilience Survey (BRS) in addition to semi-structured qualitative interviews. Screening and interviews will take place by the study coordinator and/or researchers. Once accepted into the study, the study staff will refer the participant to a member of The Open Table to implement The Open Table model (Network Table) and measure specific outcomes over the intervention period. Patient name, phone number, and email will be shared with The Open Table in order for them to contact the participants and learn more about their SDoH needs. The Network Table consists of 10 trained volunteers that will meet bi-weekly to address the patient's SDoH needs, prioritize interventions and meet with the patients as is appropriate and necessary to resolve each identified need. Once the patient's needs have been met, a seat at the table will become available and additional patients will be recruited to the table. If additional needs arise for individual patients (and there is capacity at the table) patients are welcome to rejoin the table to address additional needs throughout the 12-month study period.

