Post-intervention we will measure patient-specific outcomes including: # of hospitalizations in the prior 12 months, # of ER visits in the prior 12 months, # of primary care visits in the prior 12 months through patient interviews and use of the EMR. Patients will have SDoH screening via the CMS Accountable Health Communities Screening Tool and the Brief Resilience Scale (BRS) after completion of the intervention. We will also collect provider survey's using the Maslach Burnout Inventory.

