#### Power Analysis:

With a sample size of 30, both combinations of before/after proportions are expected to have at least 80% power, assuming we use alpha 0.05 for testing. If we correct for multiple testing (2 primary outcomes) using a Bonferroni-adjusted alpha of 0.025, both combinations of proportion assumptions are expected to have close to or above 80% power to detect a difference before vs after intervention.

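### The primary resilience outcome reads as a before/after proportion with no visible cut-point; a mean change in BRS score would make better use of the same data

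*Combined protocol and SAP*

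**What the plan says.** The Measures text under Describe approach names two primary outcomes, each taken before and after the intervention: the CMS screening tool and the BRS. Both administrations of the scale are planned. It is part of the baseline assessment, and patients complete "the Brief Resilience Scale (BRS) after completion of the intervention".

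The Statistical Analysis section gives the summary measure for both primary outcomes in one phrase: "Difference in proportion (before vs after intervention) in SDOH status and resilience score". It then offers two routes. For the first, "Differences in categorical endpoints before vs after the intervention will be tested using McNemar's test for paired proportions", with the exact version for small samples. For the second, "Differences in continuous endpoints before vs after the intervention will be tested using paired t-tests, or appropriate non-parametric test". The BRS is not assigned by name to either route, and no cut-point or responder rule for it is visible.

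The Power Analysis section speaks only of proportions. With 30 patients, "both combinations of before/after proportions are expected to have at least 80% power" at alpha 0.05. It continues "If we correct for multiple testing (2 primary outcomes) using a Bonferroni-adjusted alpha of 0.025", and says that then "both combinations of proportion assumptions are expected to have close to or above 80% power".

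**The concern.** A score becomes a proportion only after a cut-point is chosen. Two patients with very different improvements then count the same if both cross the cut, and an improvement that stays on one side of it counts as nothing. With 30 patients there is little information to spare.

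Two things are at stake. First, a moderate real gain in resilience is much more likely to be missed. Second, the answer changes with the cut, so a cut that is not fixed in advance leaves room to choose it after the data are seen. The scale is already collected before and after, so the more efficient analysis needs no new data.

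**Working it through.** **The plan's own figures.** The Bonferroni step reproduces: 0.05 / 2 = 0.025. The stated power cannot be reproduced, because the before/after proportions are not visible. It is attainable under some assumptions and not others:
- 90% to 50%, independent responses: discordant probabilities 0.9 × 0.5 = 0.45 and 0.1 × 0.5 = 0.05. Exact McNemar power is 90% at alpha 0.05 and 84% at 0.025.
- 80% to 50%, within-patient correlation 0.3: P(yes at both) = 0.8 × 0.5 + 0.3 × √(0.16 × 0.25) = 0.46, so the discordant probabilities are 0.34 and 0.04. Power is 75% and 65%.

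The stated 80% is therefore neither confirmed nor refuted.

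**Comparing the two analyses of the BRS.** From the documents: n = 30 and alpha 0.05 or 0.025. Assumed, because the plan gives none of these: all 30 pairs complete, two-sided tests, bivariate normal scores with SD 1 at both times, shift δ = 0.5 SD, correlation ρ = 0.3, 0.5 or 0.7.

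*Paired t-test.* The standardised change is d = δ / √(2(1 − ρ)). Power is the probability that a noncentral t with 29 df and noncentrality d√30 exceeds 2.045. For ρ = 0.5, d = 0.5 / √1 = 0.50 and the noncentrality is 0.50 × 5.477 = 2.739.

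*Exact McNemar.* For a cut at c, p(up) = P(pre < c, post ≥ c) and p(down) = P(pre ≥ c, post < c). The number of discordant pairs m is Binomial(30, p(up) + p(down)). Given m, the upward count b is Binomial(m, p(up) / (p(up) + p(down))). The test rejects when 2·P(Bin(m, 0.5) ≤ min(b, m − b)) ≤ alpha. Power is summed over all m and b.

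| ρ | d | Paired t | Cut at baseline mean (50% to 69%): up / down, exact power | Cut 0.5 SD below (69% to 84%): up / down, exact power |
|---|---|---|---|---|
| 0.3 | 0.423 | 61% | 0.303 / 0.112, 27% | 0.232 / 0.082, 20% |
| 0.5 | 0.500 | 75% | 0.273 / 0.082, 31% | 0.211 / 0.061, 22% |
| 0.7 | 0.645 | 93% | 0.240 / 0.049, 38% | 0.187 / 0.037, 25% |

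Ordinary McNemar without continuity correction does better but stays behind the t-test: 36-50% with the cut at the mean and 29-42% with the lower cut. At alpha 0.025 with the cut at the mean, the paired t-test has 49-87% and exact McNemar about 20-27%.

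A cut 0.5 SD above the baseline mean is the mirror image of a cut at the mean when the shift is 0.5 SD, and gives the same power. The cut-point effect therefore shows only in the comparison with the lower cut.

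**Larger shifts, alpha 0.05, cut at the baseline mean or 0.5 SD above.** At 0.8 SD: paired t 95-100%, exact McNemar 62-83%. At 1.0 SD: 99-100% and 81-96%. The gap narrows, but this depends on the cut: at 0.8 SD with the cut 0.5 SD below the mean, the same formula gives exact McNemar only 45-56%.

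**Detectable change for a score analysis.** Solving the t-test power for 80% with n = 30 gives d = 0.53 at alpha 0.05 and 0.59 at 0.025 (critical value 2.364). In baseline SDs, 0.53 × √(2(1 − ρ)) is 0.63, 0.53 or 0.41 for ρ = 0.3, 0.5 or 0.7.

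**The case against.** The strongest reply is that nothing is unsettled. The proportion wording governs both primary outcomes, the power text sets two combinations of proportions beside two primary outcomes, and the route for continuous endpoints has an obvious use in the three utilisation counts. On that view the BRS is simply binary, and a responder endpoint with a fixed cut is legitimate. Most of this stands: the proportion reading is the more natural one. It does not remove the point, because that is the reading under which information is lost and the cut matters.

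Three stronger conclusions are tempting and not supported:
- *The resilience outcome has no power statement.* This needs the less natural reading, in which the BRS is tested as a score. Under the proportion reading the power text covers it in form, although the combinations are not tied to named outcomes.
- *The plan omits the cut-point and the proportions.* The power text refers back to something not shown. A table or category definition may have been lost in extraction, so only "not visible" can be said.
- *Thirty patients are too few, or the 80% is wrong.* The 80% concerns proportions whose values are not visible, and the shift used above is assumed.

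It is also fair that this is a preliminary single-group study with feasibility as its first aim, and that the hypothesis of Aim 2 does not mention resilience. That limits the weight of the point. The BRS is still named as primary, and a formal power claim is made.

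**Conclusion.** The concern holds as a worthwhile, inexpensive improvement. As most naturally read, the plan splits a primary score at a cut that the supplied text does not show. For a moderate shift of 0.5 SD this would cost roughly 34 to 55 percentage points of power against the paired t-test with the cut at the mean (61 − 27 = 34 at correlation 0.3; 93 − 38 = 55 at 0.7), and more with the lower cut.

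These sizes rest on assumed normal scores, shift, correlation, cut and complete follow-up. A response concentrated in a few patients was not examined. The t-test itself is short of 80% at 0.5 SD when the correlation is 0.3 or 0.5; what supports the change is the ranking of the methods, not a guarantee of adequate power.

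**What to change.** Before outcome data are examined:

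1. **Statistical Analysis.** Separate the two primary outcomes. Define the primary resilience analysis as mean change in BRS score with 95% CI by paired t-test, with the Wilcoxon signed-rank test as sensitivity analysis. Keep any BRS proportion as description, with its cut-point fixed in advance.
2. **Power Analysis.** Add for this endpoint that 30 complete pairs give 80% power for a mean change of about 0.53 SD of the individual changes at two-sided alpha 0.05, or 0.59 at 0.025.
3. **If the sponsor prefers the proportion as primary.** State the cut-point in advance, name McNemar's test for this outcome, and tie the before/after proportions in the Power Analysis to that cut.

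The score analysis is a recommendation on efficiency; settling the definition is needed under either choice. The cost is wording in two sections, since the BRS is already collected at both times. The downside is that a mean change is slightly harder to explain than a proportion, which can still be shown beside it.

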We intend to implement community engagement in 2 ways. First, we will partner with a community organization/501c3 (The Open Table) to bring their model of leveraging social and relationship capital to the healthcare community. Second, we will partner with a Federally Qualified Health Center (FQHC) (Valleywise Health) to help patients with identified SDoH needs that would benefit from enhanced community-based resources. Additionally, we will partner with said FQHC to measure patient-specific impact (outcomes in relation to SDOH) and provider impact (measure impact on burnout).

Patients will be recruited to the study with the assistance of a research coordinator and in partnership with FQHC staff. This study will follow patients and providers (the healthcare team) for up to one-year post-enrollment, or until patient intervention is complete. Baseline data will be collected via structured individual patient interviews and by collecting baseline SDoH data via the CMS Accountable Health Communities Screening Tool, BRS tool. Screening data may be shared with The Open Table so they can better understand the needs of the participant. Once enrolled in the study, patients will be assigned to a Network Table of trained community volunteers that will support patients with a focus on overcoming SDoH needs to improve health. Each "table" of volunteers will be led by a project director, and each volunteer will be trained by The Open Table.

We will also recruit referring providers to the study (anticipate approximately 10 providers). These providers will be asked to complete the Maslach Burnout Index pre/post intervention.

Inclusion criteria: We will include patients that are age 18 or over with an identified SDOH need that impacts healthcare outcomes (identified by the healthcare team).

Exclusion criteria: non-english speaking patients, patients <18 years old, patients who are pregnant.

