Recruitment: Potential participants with SDOH needs that are negatively impacting their healthcare will be referred by the FQHC healthcare team. Patients meeting inclusion criteria will be referred to the research team. Recruiting providers will provide eligible patients with a flyer with the research team contact information, once the flyer is returned to the research team the patient will be contacted for consideration of enrollment and consent. The research team will obtain consent for all patients appropriate for participation in the study. Providers that refer patients to the study will be asked complete a survey of baseline and post-intervention burnout (Maslach burnout inventory).

Measures:

Our primary outcomes will be responses to the following survey questions pre/post intervention: CMS Accountable Health SDOH Screening Tool and the Brief Resilience Scale (BRS).

Secondary outcome measures will include: # of hospitalizations and # of ER visits, # of primary care visits and perceived access to nutritious food, healthcare worker and/or social worker burnout evaluations (pre/post). Additionally, we will complete semi-structured qualitative interviews of each participant pre/post to determine the impact of this intervention on other aspects of their life/health.

Tertiary measures will be provider burnout scores pre and post intervention based on the Maslach Burnout Inventory.

We will obtain baseline data on # of hospitalizations in the prior 12 months, # of ER visits in the prior 12 months, # of primary care visits in the prior 12 months through patient interviews and use of the EMR. Patients will have SDoH screening via the CMS Accountable Health Communities Screening Tool at baseline. Additionally, each enrolled patient will be interviewed at baseline to understand their responses to the primary outcome measurements. To better understand the patient-specific variables that may contribute to SDoH challenges and outcomes we will also collect patient demographics (e.g., age, gender, race, ethnicity, marital status), medical information (e.g., medical comorbidities, current medications), socioeconomic status (e.g., education, income, employment), environmental data (e.g., address, census measures). Provider surveys will be collected using the Maslach Burnout Inventory.(pre and post intervention). These data will be collected via the electronic medical record, survey data from patients, and survey data from medical providers and healthcare staff.

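### The primary SDOH outcome is an undefined yes/no status in patients enrolled for having a need: it would miss partial gains, and a significant change could not be credited to the intervention

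*Combined protocol and SAP*

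**What the plan says.** **Entry.** In the approach section, the inclusion criterion reads "We will include patients that are age 18 or over with an identified SDOH need that impacts healthcare outcomes". The judgement belongs to clinic staff: "These patients will have an identified SDOH need that is negatively impacting their health (as determined by the FQHC staff". The tool comes afterwards: "Once referred, the patient will be screened with a SDOH screening tool". No tool score or threshold is required for entry.

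**Design.** There is one group, all receiving the Network Table: "We aim to recruit 30 patients (total) into this study to power the results sufficiently". No comparator is described.

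**Primary outcome.** Under Measures: "Our primary outcomes will be responses to the following survey questions pre/post intervention", followed by the names of the SDOH screening tool and the Brief Resilience Scale (BRS). Under Statistical Analysis: "Difference in proportion (before vs after intervention) in SDOH status and resilience score". SDOH status is not defined as any need, number of needs or need per domain.

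**Test.** Differences in categorical endpoints "will be tested using McNemar's test for paired proportions, or exact McNemar's test for small sample sizes". Continuous endpoints get a paired t-test or a non-parametric alternative.

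**Power.** The Power Analysis claims at least 80% power with 30 patients, "assuming we use alpha 0.05 for testing", and close to or above 80% at 0.025 if a correction for two primary outcomes is made. The before/after proportions behind the claim are not given.

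**Claim to be supported.** The Aim 2 hypothesis is causal: support through the Open Table model is expected to reduce SDOH needs.

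**The concern.** Selecting patients on the condition that is then measured affects a yes/no outcome in two ways.

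First, if status means any need, most patients start positive and change status only when their last need clears. A patient who goes from three needs to one is recorded as unchanged, so a useful intervention could look ineffective.

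Second, when nearly everyone starts positive, there is little room to move except towards improvement. Needs that resolve, or are answered differently, without the intervention all count in its favour. With no comparison group, the analysis cannot separate these from an intervention effect, yet Aim 2 reads the change causally.

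In addition, Measures and Statistical Analysis describe the SDOH outcome differently and neither fixes one endpoint. The definition could therefore be chosen after the data are seen, while the Power Analysis counts only two primary outcomes.

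**Working it through.** **Inputs from the documents:** 30 patients, one group; entry on an identified need; McNemar or exact McNemar; alpha 0.05, or 0.025 if corrected.

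**Assumptions:** two-sided testing, no dropout, and all resolution and new-need rates below. The documents give none of these.

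**1. The plan's own power figure.** It cannot be reproduced, because neither the before/after proportions nor the share of patients who change status is given. An assumed fall from 0.90 to 0.60 with n = 30 has exact McNemar power of 68% (alpha 0.05) and 59% (0.025) if the two assessments are independent. It has 92% and 84% if all change is one-way. So 80% is attainable for some inputs but cannot be checked.

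**2. Rejection threshold with everyone positive at baseline.** If b patients clear all needs and none can move the other way, exact two-sided p = 2 × 0.5^b.
- b = 5: 0.0625
- b = 6: 0.031, significant at 0.05
- b = 7: 0.016, significant at 0.025

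**3. Chance of significance with no intervention effect.** If a share r of patients would clear all needs anyway, this is P(X ≥ 6) or P(X ≥ 7) with X ~ Binomial(30, r).

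| r (assumed) | alpha 0.05 | alpha 0.025 |
|---|---|---|
| 5% | 0.3% | 0.1% |
| 10% | 7% | 3% |
| 15% | 29% | 15% |
| 20% | 57% | 39% |

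An exact ceiling is not needed. With 20% resolving and 10% new needs among those without one, the alpha 0.05 figures are 47%, 38% and 23% at baselines of 95%, 90% and 80%. When flows in the two directions are equal (5% to 20% of patients each way), rejection stays at or below 2.4%. The excess therefore comes from selecting on need without a comparator, not from McNemar's test.

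**4. Sensitivity to partial gains.** Assume five independent domains, each with prevalence 0.4, in patients with at least one need; 40% of needs resolve and 5% of need-free domains gain one.
- A domain is need-free at follow-up with probability 0.6 × 0.95 + 0.4 × 0.4 = 0.73.
- It is need-free at both times with probability 0.6 × 0.95 = 0.57.
- P(all clear at follow-up, given at least one need at baseline) = (0.73^5 − 0.57^5) / (1 − 0.6^5) = (0.2073 − 0.0602) / 0.9222 = 0.160.
- McNemar on any need: P(X ≥ 6) with X ~ Binomial(30, 0.160) is about 34%.
- Count: mean baseline needs are 5 × 0.4 / 0.9222 = 2.17. The mean fall is 2.17 × 0.4 − 2.83 × 0.05 = 0.73. By simulation, a paired t-test on the count rejects about 99% of the time at 0.05.

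**5. Does the count remove the attribution problem?** No. In the same model with 20% of needs resolving, 5% new and no intervention effect, the chance of clearing all needs is (0.65^5 − 0.57^5) / 0.9222 = 0.061. McNemar on any need then rejects about 1% of the time, and the count test about 57%. The count detects change better, whatever causes it.

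**6. Power for the count.** With 30 complete pairs, a paired t-test has 80% power for a change of about 0.53 SD at alpha 0.05, or 0.59 SD at 0.025.

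**The case against.** **McNemar's test is sound.** A reader might infer that the planned test has an invalid error rate. It does not. The stated target is a before/after difference in proportion. If needs resolve for any reason, the proportions do differ and rejection is correct. The percentages in step 3 are chances of detecting a real change that the intervention may not have caused. This objection stands in full.

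**The ceiling is inferred.** A reader might take baseline to be 100%. The documents do not say so. Staff judgement, not the tool, qualifies patients, so some may screen negative. If status means a single domain such as housing, baseline could be well below 100% and the bias smaller.

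**The turnover rate is unknown.** At 5% per patient the excess is negligible. Moreover, the rate in step 3 requires every need to clear, which is rarer than one need resolving.

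**Item-by-item testing is not planned.** The wording about responses to survey questions might suggest many primary tests and an inflated family-wise error. However, Measures names two instruments, the Power Analysis counts two outcomes, and no section describes separate item tests. What stands is only that a single SDOH endpoint is not fixed.

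**This is a preliminary study.** Feasibility is Aim 1, and the plan already allows paired t or non-parametric tests. That lowers the severity. It does not excuse an undefined primary outcome or the causal hypothesis in Aim 2.

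**Conclusion.** The concern holds in a limited form and should be fixed.

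- **Insensitivity:** if status means any need, the outcome misses partial gains (about 34% against 99% rejection). The size rests on the assumed five-domain model.
- **Attribution:** a significant change cannot be credited to the intervention. The chance of one without any effect runs from 0.3% to 57% for assumed per-patient resolution of 5% to 20%, at alpha 0.05 with everyone positive at baseline. The approach section may add to this, because a place at the table ends once needs are met and the post-intervention assessment follows completion. The follow-up measurement can thus be prompted by the outcome itself.
- **Definition:** Measures and Statistical Analysis leave the SDOH endpoint open.

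The fault lies in the undefined endpoint and the causal interpretation, not in the choice of McNemar's test.

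**What to change.** 1. In Measures and Statistical Analysis, define the primary SDOH outcome as the number of screening-tool domains with an unmet need per patient, counting both new and resolved needs. Test the paired change by paired t-test or Wilcoxon signed-rank test at alpha 0.025, naming which in advance. Make the mean BRS score the second primary outcome, also at 0.025.
2. Report any need, and each domain, as before and after proportions with 95% confidence intervals.
3. State that the count does not remove regression to the mean or background turnover. State that both primary results will be reported as change from baseline and not as evidence of an intervention effect, and align the Aim 2 wording.

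**Cost:** wording only, with no new data collection. The proportion-based power claim would no longer apply to these outcomes. It should be restated as 80% power for a paired change of about 0.53 SD (alpha 0.05) or 0.59 SD (alpha 0.025) with 30 complete pairs.

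### The post window for hospitalizations, ER visits and primary care visits is not defined for patients who finish before 12 months, and a look-back taken at completion would re-count baseline months

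*Combined protocol and SAP*

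**What the plan says.** All places are in the combined protocol and SAP.

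- **Baseline count** (Describe approach, Measures): "We will obtain baseline data on # of hospitalizations in the prior 12 months". ER and primary care visits have the same window, and the sources are patient interviews and the EMR.
- **Post count, measurement text** (Describe approach, after Measures): "Post-intervention we will measure patient-specific outcomes including: # of hospitalizations in the prior 12 months". No calendar date is attached. The next sentence places the SDOH tool "and the Brief Resilience Scale (BRS) after completion of the intervention".
- **Post count, analysis text** (Statistical Analysis): "Difference in number of hospitalizations in the 12 months before vs 12 months during intervention", repeated for ER and primary care visits. Continuous endpoints go to a paired t-test or a non-parametric test. No rate or person-time adjustment is mentioned.
- **Length of intervention** (Describe approach, Network Table paragraph): it is set by need. Once a patient's "needs have been met, a seat at the table will become available" to others, though "patients are welcome to rejoin the table to address additional needs throughout the 12-month study period".
- **Follow-up** (Describe approach, community engagement paragraphs): patients are followed "for up to one-year post-enrollment, or until patient intervention is complete".

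**The concern.** The analysis text presumes that every patient has 12 months of intervention, but the design expects some to finish sooner. For them the analysis window does not exist. The measurement text then supplies a different rule, a 12-month look-back from an unstated date. If that date is the day of completion, part of the post count consists of pre-enrolment months that are also in the baseline count. The same events then sit on both sides of the paired difference, and the post figure is not a post-enrolment count. Two analysts following the text could obtain different counts from the same patient.

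Hospitalizations and access to care are named interests of Aim 2, and fewer hospitalizations and ER visits are among the expected results under Describe Outcomes. These are nevertheless secondary outcomes of a 30-patient preliminary study.

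**Working it through.** **The plan's own figure.** The only power statement (Power Analysis: n = 30, at least 80% at alpha 0.05) concerns before/after proportions for the primary outcomes. It gives no input for the visit counts and does not depend on their window, so there is no figure to reproduce for this point.

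**Window arithmetic.** Put enrolment at month 0 and completion at month T.

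- Baseline window: −12 to 0.
- Look-back taken at completion: T − 12 to T.
- Overlap: 12 − T months, which is 8 months at T=4, 6 at T=6, 3 at T=9 and none at T=12.

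**Apparent change if the effect persists.** Assume a constant baseline rate and a rate ratio R that holds from enrolment to month 12. The look-back ratio for an early finisher is ((12 − T) + R·T)/12. With R = 0.5 and T = 6 it is (6 + 3)/12 = 0.75, a 25% fall instead of 50%. With a share s finishing at T, the trial-level change is the true change × [1 − s(1 − T/12)]. For a true 50% fall:

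| T | s=20% | 30% | 50% | 100% |
|---|---|---|---|---|
| 4 | 43% | 40% | 33% | 17% |
| 6 | 45% | 42.5% | 37.5% | 25% |
| 9 | 47.5% | 46% | 44% | 37.5% |

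**Apparent change if use returns to baseline at completion.** Months T to 12 then run at the baseline rate. The fixed window from enrolment to month 12 has ratio (R·T + (12 − T))/12, which is the same expression. Both windows show the same apparent change.

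**Power.** Assumed inputs: n = 30, patient rates gamma with shape 1 and mean 2 a year, Poisson counts, 50% fall, paired t-test at 0.05, 20,000 simulated trials per cell. Overlapping months are the same simulated events in both counts. Entries are for s = 20/30/50/100%.

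| T | Look-back at completion (either case) | Fixed window, effect persists | Fixed window, use returns to baseline |
|---|---|---|---|
| 4 | 76/72/63/39% | 82% | 68/59/43/14% |
| 6 | 78/75/69/54% | 82% | 71/65/54/27% |
| 9 | 80/79/77/70% | 82% | 77/75/69/55% |

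Repeat runs agree to about one percentage point. The look-back column is the same in both cases because it never sees months T to 12. In the last column the look-back has more power because the shared events cancel in the difference.

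At mean 1 a year with a persistent effect, T=6 gives 49/47/42/30% against 54%. For a persistent 50% rise in primary care visits at mean 2, T=6 gives 56/53/49/36% against 61%. With no effect and constant rates, the rejection rate is 4–5% throughout.

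**Illustration only, non-constant rates.** The pattern is constructed and has no basis in the documents. Suppose T = 6, use doubles within the baseline year (0.67 then 1.33 events, total 2.00), and the year after enrolment is 25% lower (1.50). The look-back holds 1.33 + 0.75 = 2.08 events, so −25% appears as +4% if all finish early. If half do, the mean is (2.08 + 1.50)/2 = 1.79, about −10%.

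**The case against.** **A month-12 count is a fair reading.** The sentence on completion governs the surveys, not the visit counts. The EMR can be read at any date, the analysis text states equal 12-month windows, and the right to rejoin within a 12-month study period means that a freed seat need not be final completion. If everyone is counted at month 12, nothing overlaps. This stands as a possible reading, so the overlap is conditional. But no sentence commits to that date, and the follow-up rule allows follow-up to stop at completion.

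**Three stronger readings that a reader might infer are not supported.**

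1. *That a fixed window would recover lost power.* This holds only if the effect outlasts table support. The documents do not say that it does, and if use returns to baseline the ordering reverses.
2. *That the look-back produces false positive findings.* Suppose a flat baseline of 2 events a year, use 50% lower in months 1–6 and 50% higher in months 7–12, with all finishing at month 6. The look-back gives 1.0 + 0.5 = 1.5 events (−25%), while the year after enrolment gives 0.5 + 1.5 = 2.0 (no change). But the fall during the intervention is real, and the analysis text asks about that period. The two windows answer different questions, so neither result is simply false.
3. *That T months will be compared raw with 12, creating a reduction where there is none.* The text on follow-up is not a counting rule. The measurement and analysis texts both specify 12 months.

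**The fix changes the question.** For early finishers, a year from enrolment includes time after support ends. This is correct and is disclosed with the fix.

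**Conclusion.** The point holds for the three utilization counts. For a patient finishing before month 12, the analysis window cannot be formed. The look-back, if taken when follow-up is allowed to end, carries 12 − T baseline months into the post count. That is an invalid before/after comparison for those patients, whichever way it moves the result.

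The size cannot be fixed from the documents, because T, the share finishing early, the event rates and the persistence of effect are all assumed here. With a persistent effect, the loss at T = 9 is at most 5 points of power for s up to 50%. At T = 6 it runs from 4 points (s=20%) to 28 (s=100%). Without persistence there is no loss relative to a fixed window.

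Severity is minor to should-fix. The primary outcomes and the Power Analysis statement are untouched.

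**What to change.** Make three wording changes, before post counts are collected:

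1. In the post-intervention measurement text of Describe approach, replace the undated look-back with the number of events in the 12 months after enrolment, for all three counts.
2. In Statistical Analysis, compare the 12 months before enrolment with the 12 months after enrolment.
3. In the follow-up sentence of Describe approach, state that early completion does not shorten the window for the utilization counts.

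Use interviews and the EMR in the same way before and after. If a patient has less than 12 months of data after enrolment, compare rates per person-time and do not fill the window with baseline months.

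Cost: counts for early finishers wait until month 12 and need a record check and a count question then, and some patients will be harder to reach. The question also becomes use in the year after enrolment, including time after table support has ended. The plan should say so.
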